5.4.2. Main Analytical Approach

[figure not shown]
The secondary effectiveness endpoints will be analyzed using Fisher's exact test based on mITT population as observed.

The exact binomial 95% CI will be provided for the proportion of responders within each treatment group. For comparison of treatment group versus control group at Week 24, the responder rate difference, 95% exact unconditional CI for risk difference, and p-value from 2-sided Fisher's exact test will be presented.

Secondary effectiveness analyses are summarized in Table 5–3.

Table 5–3 Secondary Effectiveness Analyses

| Endpoint | Description | Timing | Methodology | |
|---------------------------|--|---------|---------------------|--|
| Responder status based on | nder status based on Number (%) of responders by Week 24 | | Fisher's exact test | |
| GAIS by EI | treatment group | WCCK 24 | Fisher's exact test | |
| Responder status based on | Number (%) of responders for | Week 24 | Fisher's exact test | |
| GAIS by participant | treatment group | WEEK 24 | risher s exact test | |
| Responder status based on | Number (%) of responders for | Week 24 | Eigher's exect test | |
| NSS by participant | treatment group | week 24 | Fisher's exact test | |

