4.4.3 Escape Medications

Administration of hyaluronidase must not be performed during this study.

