6.2.3 Post-control Period

6.2.3.1 Treatment Group Subjects

For treatment group subjects, routine follow-up visits for safety and effectiveness will occur at Weeks 36 and 48 after the last treatment (initial or touch-up). 3D digital images as well as the GAIS, assessed separately by the EI and the subject, will be performed in addition to the subject assessment of satisfaction with the treatment outcome using the NSS and the subject's willingness to recommend the treatment to a friend. Vital signs will be collected at all visits.

Any treatment group subject who withdraws from the study prior to the Week 48 visit must undergo the procedures scheduled for Week 48 at his/her last on-site visit. A urine pregnancy test must be conducted at study exit or at the time of withdrawal if the subject withdraws from the study prior to the Week 48 visit. The procedures to be performed during the post-control period are specified in [Table 2](#).

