6.6 Withdrawal Criteria

The subject may withdraw at will at any time for any reason.

If a subject has a positive urine pregnancy test prior to initial treatment, the subject will not be eligible for treatment and will be withdrawn from the study. If a subject has a positive urine pregnancy test after treatment, she will continue all scheduled visit and non-treatment procedures. The pregnancy will be followed as described in Section 10.3. If a subject receives hyaluronidase or dermal fillers in the nose area during the trial, s/he will be withdrawn from the study.

7. Response Measures and Summary of Data Collection Methods

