Every attempt will be made to collect complete data and limit the occurrence of missing data. Imputation of missing data will be performed for the primary effectiveness analysis as a sensitivity analysis.

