1.1. Objectives and Endpoints

| Objective | | | | | |
|---|---|---|--|--|--|
| Clinical | Statistical | | | | |
| Category | Category | Estimand/Variable | | | |
| Primary Objecti | ve: to evaluate th | ne safety and effectiveness of VOLUMA with Lidocaine injectable gel for the | | | |
| improvement of v | olume and aesthe | etic appearance of the nose in a Chinese population. | | | |
| Effectiveness ¹ | Variable: change from baseline in the nose volume calculated by | | | | |
| | | digital analysis of each participant's 3D images at Week 24 | | | |
| | | Population: mITT | | | |
| | | • IES: | | | |
| | | Missing at random will be assumed in an MMRM model, | | | |
| | | therefore no imputation will be conducted | | | |
| PLS: change from baseline between treatment and MMRM | | • PLS: change from baseline between treatment and control groups | | | |
| | | o MMRM | | | |
| | Secondary | Variable: GAIS responder by EI and participant, NSS responder by | | | |
| | | participant at Week 24 | | | |
| | | Population: mITT | | | |
| | | • IES: | | | |
| | | Participants with missing data at Week 24 will not be imputed | | | |
| | | PLS: responder rates between treatment and control groups | | | |
| | | o Fisher's exact test | | | |
| Safety | Primary | Variable: | | | |
| | | o TEAEs | | | |
| | | o ISRs | | | |
| | | Population: Safety Population | | | |
| | | Analysis: Categorical descriptive | | | |

IES = Intercurrent event(s) strategy; PLS = Population-level summary.

¹ All estimand attributes explicitly identified for primary/secondary and select key estimands only.

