A sample size of 90 treatment and 30 control participants will provide 99.6% power to detect a difference of 0.9 mL in the mean volume change from baseline between the treatment and control group, assuming a mean change from baseline of 1.1 mL with standard deviation of 0.9 mL, and mean change from baseline of 0.2 mL with standard deviation of 0.9 mL, for the treatment and control groups, respectively. This calculation is based on a 2-sample, 2-sided t-test at 5% significance level. The assumptions of means and standard deviations are estimated from Allergan studies VOLXC-AP-ND-001 and VOLUMA-004. In order to have over 100 treatment group participants complete 1-year follow-up, accounting for participant attrition of 15% during the whole study duration through Week 48, at least 120 participants in the treatment group and 40 participants in the control group will be randomized.

4. Populations for Analysis

The analysis populations will consist of participants as defined in Table 4–1:

Table 4–1 Analysis Populations

| Population | Definition | Study Treatment | |
|---|--|--------------------|--|
| mITT Population | mITT Population All participants who are randomized and have at least 1 assessment of change from baseline in nose volume | | |
| PP Population | All mITT participants who have baseline and Week 24 assessments of | | |
| Safety Population | All randomized participants who receive VOLUMA treatment in the Control Period or who do not receive VOLUMA treatment in the Control Period and with at least 1 follow-up assessment | As treated | |
| VOLUMA Initial Treated Population (VITP) | Participants randomized and received VOLUMA treatment in the Control Period with up to 48 weeks follow-up | As treated | |
| VOLUMA Optionally Treated Population (VOTP) | Participants randomized to control group and received optional VOLUMA treatment in Post-Control Period. These participants will have up to 24 weeks follow-up after optional VOLUMA treatment (or touch-up treatment). | As treated | |

JUVÉDERM® VOLUMA® with Lidocaine

5. Statistical Analyses

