- Descriptive statistics for continuous variables include the sample size (n), mean, standard deviation, median, 1st and 3rd quartiles, minimum, and maximum.
- Summary statistics for categorical variables include the sample size (N1), frequency count, and percentage.
- Partial dates will be treated as missing in computations but listed in the data listings as they appear on the eCRFs unless otherwise specified. No imputation of missing values will be performed, unless otherwise specified.
- The level of significance used for all statistical tests will be 0.05, 2-sided, unless stated otherwise.
- The change from baseline values will be computed as the value for the post baseline visit minus the baseline value, unless otherwise indicated.
- All statistical analysis will be performed using SAS version 9.3 or higher.
- MedDRA will be used to code adverse events and medical history.
- WHO Drug Dictionary will be used to code medications.

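### Week 24 GAIS and NSS responder rates use observed ratings only, with no rule for participants withdrawn after hyaluronidase or another nasal filler; if such withdrawals occur before Week 24, the treatment-group rate is biased upward

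*SAP*

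**What the plan says.** **Analysis.** The three secondary endpoints are the Week 24 responder proportions for GAIS by the evaluating investigator (EI), GAIS by the participant, and NSS by the participant. SAP 5.4.2: "The secondary effectiveness endpoints will be analyzed using Fisher's exact test based on mITT population as observed". The intercurrent-event entry for these endpoints in SAP 1.1 reads: "Participants with missing data at Week 24 will not be imputed". That is a missing-data rule and names no event.

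**Withdrawal.** Protocol 6.6: "If a subject receives hyaluronidase or dermal fillers in the nose area during the trial, s/he will be withdrawn from the study". Protocol 4.4.3 says: "Administration of hyaluronidase must not be performed during this study". Protocol 4.4.2 also bars other nasal fillers, though it contemplates that a prohibited treatment may be given with participant safety as the first consideration.

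**Exit assessment.** Protocol 6.2.3.1: "Any treatment group subject who withdraws from the study prior to the Week 48 visit must undergo the procedures scheduled for Week 48". Those procedures include GAIS and NSS. SAP 6.4.1.1 (Table 6-3) then assigns ratings by day after the most recent treatment: Days 2 to 85 to Week 8, Days 86 to 141 to Week 16, and Days 142 to 211 to Week 24.

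**Population.** SAP Section 4 (Table 4-1) defines mITT as: "All participants who are randomized and have at least 1 assessment of change from baseline in nose volume". Protocol 8.1 instead asks for at least one effectiveness assessment of any kind and, in the treatment group, at least one device treatment. SAP Appendix 2 discloses the change and explains it by the primary variable.

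**Sensitivity analyses.** Protocol Section 8: "Imputation of missing data will be performed for the primary effectiveness analysis as a sensitivity analysis". SAP 5.3.3 likewise covers the primary endpoint only.

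**The concern.** A responder endpoint needs a rule for participants who did not reach the assessment on the assigned treatment. Here one cause of missingness can be linked to the outcome: someone whose filler was dissolved, or who had another product placed in the nose, is withdrawn, and the plan does not say how that person counts. If the exit visit falls before Day 142, the exit rating is filed under Week 8 or Week 16 and the person vanishes from the Week 24 proportion.

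The proportion itself is the evidence. Protocol 8.3.2 defines the secondary results as treatment-group rates with exact 95% CIs. Protocol 6.2.2.3 schedules only 3D imaging and EI-assessed GAIS for controls during the control period. For participant GAIS and NSS, the treatment-group rate and its interval are therefore essentially the whole result.

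A smaller, separate issue is that the SAP's mITT requires a volume change. A participant with observed ratings but no usable volume change at any visit is excluded from endpoints that do not use volume.

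**Working it through.** **1. The plan's own figures.** SAP Section 3 gives 90 versus 30 participants, a difference of 0.9 mL, SD 0.9 mL, a two-sided 5% t-test and 99.6% power. The noncentrality is 0.9 / (0.9 × √(1/90 + 1/30)) = 4.74. With 118 degrees of freedom the power is 99.7%, so the figure reproduces closely. The completers also reproduce: 120 × 0.85 = 102 and 160 × 0.85 = 136. No responder rate or power is stated for GAIS or NSS, so what follows needs assumptions.

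**2. Who leaves the denominator.**

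| Exit rating, days after last treatment | Assigned to | Counted at Week 24? |
|---|---|---|
| 2 to 141 | Week 8 or 16 | No |
| 142 to 211 | Week 24 | Yes |
| After 211 | Week 36 or 48 | Week 24 visit normally already done |

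The gap is therefore withdrawal before Day 142, or withdrawal without any rating on Days 142 to 211.

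**3. Size.** Let 120 be treated (SAP Section 3), k withdrawn under protocol 6.6 with no Week 24 rating, all others observed, and x responders.

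- As observed: p = x / (120 − k).
- With the k counted as non-responders: x / 120.
- Difference: p × k / 120.

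Assumed values, not in the documents: p from 60% to 90%, and k as shown.

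| k | Difference at p = 60% | Difference at p = 90% |
|---|---|---|
| 1 | 0.5 points | 0.75 points |
| 3 | 1.5 | 2.25 |
| 6 | 3.0 | 4.5 |
| 18 | 9.0 | 13.5 |

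The last row is a ceiling, not an expectation. It treats all of the planned 15% attrition (120 × 0.15 = 18) as protocol 6.6 withdrawals before Week 24, whereas that figure is all-cause and runs through Week 48.

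Examples with exact (Clopper-Pearson) 95% CIs:

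- k = 3: 94/117 = 80.3% (72.0 to 87.1) becomes 94/120 = 78.3% (69.9 to 85.3).
- k = 6: 103/114 = 90.4% (83.4 to 95.1) becomes 103/120 = 85.8% (78.3 to 91.5).
- k = 18: 92/102 = 90.2% (82.7 to 95.2) becomes 92/120 = 76.7% (68.1 to 83.9).

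**4. Interval width.** The as-observed interval is not always the narrower one. With 66 responders, 66/110 has a width of 19.0 points and 66/120 a width of 18.4.

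**5. Effect on the EI GAIS test.** Take 102 observed and 18 missing in the treatment group, observed rates of 60, 80 or 90%, and 0, 3 or 7 assumed control responders of 34 (40 × 0.85). Counting all 18 as non-responders leaves the two-sided Fisher p-value below 0.002 in every case. The issue concerns the reported rate and its interval more than the test.

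**The case against.** The case on the other side is substantial.

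- **The events may not happen.** Protocol 4.4.2 and 4.4.3 bar both triggers. A reader might infer that the rates are in fact inflated. The documents give no count and do not support that; the bias is conditional.
- **The event is not proof of non-response.** A reader might infer that anyone whose filler was dissolved or supplemented failed treatment. On the trial's own GAIS (protocol Table 4), grade 1 counts as response yet describes an improved nose for which more treatment is called for. Seeking more filler is compatible with GAIS response, and the documents do not say why hyaluronidase would be given. Making a composite rule the main analysis is an estimand choice, not the correction of an error.
- **The SAP follows the protocol.** Protocol 8.3.2 already specifies observed rates and plans imputation for the primary analysis only. It sets no success threshold for these rates.
- **The mITT effect is narrow.** A reader might infer that a rating is lost whenever an image fails. One volume change at any visit is enough, so a rating is lost only if the baseline image or every post-baseline image is unusable. Protocol 6.4 allows repeat imaging, and SAP version 2 widened the control-group baseline definition to keep participants affected by an imaging set-up error.
- **Part of the SAP is not visible.** The text passes from 5.4 to 5.6, so a further analysis cannot be wholly excluded. The no-imputation entry in SAP 1.1 makes one for these endpoints unlikely.

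All of this limits the size and certainty of the point. None of it supplies a rule for these participants, and the exit visit does not either, because of the day windows.

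**Conclusion.** The gap holds in conditional form. The visible plan sets no strategy for the protocol 6.6 events. A treated participant withdrawn for one before Day 142 drops out of the Week 24 proportion. If such events occur and are regarded as non-response, the as-observed treatment-group rate is too high by p × k / 120.

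That is about 0.5 to 4.5 points for 1 to 6 events among 120, assuming observed rates of 60 to 90% and no other missing ratings. With no events the shift is zero. It does not follow that the exact interval is always too narrow, or that the EI GAIS comparison is at risk.

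The SAP's mITT adds a small, avoidable loss of ratings for participants without any usable volume change; the documents give no basis for sizing it. This is a low-cost improvement to the secondary analyses and does not affect the primary result.

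**What to change.** In SAP 5.4.2:

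1. Keep the as-observed analysis. Add, for all three responder endpoints, a sensitivity analysis that counts every treated treatment-group participant without a Week 24 rating as a non-responder. Its denominator should be all treated treatment-group participants, including anyone withdrawn before a first effectiveness assessment. Report beside it the number withdrawn under protocol 6.6 before Week 24, so that readers can separate these from other missing ratings.
2. Run the GAIS and NSS analyses on the protocol's mITT. In the treatment group this means randomized, at least one device treatment and at least one effectiveness assessment; in the control group, randomized and at least one effectiveness assessment. A participant with observed ratings but no usable 3D volume change is then kept.

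Separately, protocol 4.4.3 (no hyaluronidase during the study) and protocol 6.6 (withdrawal if it is received) should be reconciled.

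**Cost.** SAP wording and one extra row per responder table; withdrawal dates and reasons are already on the eCRF (protocol 6.5). The sensitivity rate may be lower, and it is deliberately conservative because it counts all missing ratings. For example, with 10 of 120 missing for any reason, 99/110 = 90.0% (82.8 to 94.9) becomes 99/120 = 82.5% (74.5 to 88.8). The secondary population may differ slightly from the primary one, which should be stated.

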5.6. Safety Analyses

5.6.1. Extent of Exposure

Treatment exposure-related variables will be summarized for the VITP and VOTP, respectively. The summary will be performed for initial treatment, touch-up treatment, and by treatment area as described in Table 5–5.

JUVÉDERM® VOLUMA® with Lidocaine

Table 5–5 Exposure to Study Treatment

| Endpoint | Description | Timing | Methodology | |
|--|---|-------------------|--------------------------|--|
| Volume injected | | | | |
| • Total | | Initial, Touch-up | Continuous descriptives | |
| Nasal dorsum | Summary by treatment group, treatment | | | |
| Columella | (initial or touch-up), and treatment area | | | |
| Anterior nasal spine | | | | |
| Treatment sites | | | | |
| • Total | | | C + : 1 | |
| Nasal dorsum | Summary by treatment group, treatment | Initial, Touch-up | Categorical descriptives | |
| Columella | (initial or touch-up) | | | |
| Anterior nasal spine | | | | |

5.6.2. Administration of Study Treatment

Variables related to administration of treatment will be summarized for the VITP and VOTP, respectively. The summary will be performed for initial treatment, touch-up treatment, and by treatment area as described in Table 5–6.

Table 5–6 Administration of Study Treatment

| Endpoint | Description | Timing | Methodology |
|---|---|----------------------|----------------------------|
| Pre-treatment Anesthesia type | Summary by treatment group, treatment (initial or touch-up) | Initial, Touch-up | Categorical descriptives |
| Pre-treatment anesthesia duration (minutes) • Anesthesia duration is computed as injection time minus start of anesthesia administration time. Summarize by treatment group, treatment, and anesthesia type. | Summary by treatment group, treatment (initial or touch-up) | Initial, Touch-up | Continuous descriptives |
| Treatment administration • Planes of injection • Device/Needle problem or malfunction | Summary by treatment group, treatment (initial or touch-up), and treatment area | Initial, Touch-up | Categorical descriptives |
| Treatment Characteristics Injection ease Product moldability | Summary by treatment group, treatment (initial or touch-up), and treatment area | Initial, Touch-up | Categorical descriptives |

5.6.3. Adverse Events

An AE will be considered a TEAE if the AE began or worsened (increased in severity or became serious) on or after the date (and time, if known) of the initial treatment for treatment group and after randomization for control group.

An AE will be considered a TESAE if it is a TEAE that additionally meets any SAE criterion.

TEAEs will be summarized by treatment group for CP using the Safety population.

TEAEs will also be summarized for TP using VITP and VOTP, respectively.

The number and percentage of participants with TEAEs as well as the events in the following AE categories will be summarized for the above populations as described in Table 5-7.

If more than 1 AE is coded to the same preferred term for the same participant, the participant will be counted only once for that preferred term using the most severe and most related occurrence for the summarizations by severity and by relationship to study intervention.

Listings of all TEAEs, TESAEs, TEAEs leading to discontinuation, and death will be presented.

Table 5-7 TEAE Summaries

| Endpoint | Description | Timing | Methodology |
|--------------------------------|--|--------|--|
| Overall summary | Overall summary only for the following categories: TEAEs Treatment-related TEAEs Treatment-related TEAEs at injection site Treatment-related TEAEs not at injection site TESAEs Treatment-related TESAEs Treatment-related TESAEs Treatment-related TESAEs at injection site Treatment-related TESAEs not at injection site Discontinued due to TEAE Deaths | CP, TP | Categorical descriptives, event descriptives |
| TEAEs | Overall summary and by SOC and PT Overall summary and by SOC, PT, and maximum severity | CP, TP | Categorical descriptives, event descriptives |
| Treatment-related TEAEs | Overall summary and by SOC and PT Overall summary and by SOC, PT, and maximum severity Overall summary by maximum severity, time to onset, duration, action taken and outcome | CP, TP | Categorical descriptives, event descriptives |
| TESAEs | Overall summary and by SOC and PT | CP, TP | Categorical descriptives, event descriptives |
| AEs leading to discontinuation | Overall summary and by SOC and PT | CP, TP | Categorical descriptives, event descriptives |

SAP 1894-701-008 amendment 1

5.6.4. **Injection Site Response**

ISRs recorded in participant diaries after each treatment (initial and touch-up) will be summarized for the VITP and VOTP, respectively. The summaries of below endpoints will be performed for initial treatment, touch-up treatment by pre-defined symptoms as described in Table 5-8.

Table 5-8 **ISR Analyses**

| Endpoint | Description | Timing | Methodology |
|--------------|---|-------------------|--------------------------|
| ISR severity | Maximum reported severity. For combined initial and touch-up, use the maximum severity of the 2 treatments. | Initial, Touch-up | Categorical descriptives |
| ISR duration | Duration from first instance of the symptom to the last instance of the symptom within the treatment period, where last instance means no further symptoms till the end of the 56-day diary period. Duration is derived as date of last ISR minus date of first ISR plus one. | Initial, Touch-up | Categorical descriptives |
| Ongoing ISR | ISR ongoing at end of the 56-day diary period, including ISR, severity, start date, end date. | Initial, Touch-up | Listing |

ISR day will be derived as ISR date – most recent treatment date + 1.

5.6.5. **Procedural Pain**

Participant assessment of procedural pain (pain during injection) on an 11-point scale ranging from 0 (no pain) to 10 (worst pain imaginable) after each treatment (initial and touch-up) will be summarized for the VITP and VOTP, respectively. The summary will be performed for initial treatment, touch-up treatment as described in Table 5-9.

Table 5-9 **Procedural Pain Analyses**

| Endpoint | Description | Timing | Methodology |
|-----------------|--|-------------------|------------------------|
| Procedural pain | Summary of pain scores as continuous scale | Initial, Touch-up | Continuous descriptive |

JUVÉDERM® VOLUMA® with Lidocaine

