2.2 Risk and Benefit

The injection procedure, anesthetic agents, or VOLUMA with Lidocaine may cause some of the risks and/or discomforts listed below. Unforeseeable risks or results are also a possibility. The risk of developing a serious complication is small. If a complication occurs, subjects will be advised to contact the Treating Investigator (TI) who will use his/her medical judgment to do whatever is necessary to treat the subject. As with any skin injection, risks can be posed by the injection procedure itself, the anesthetic agent, and injection of VOLUMA with Lidocaine. Risks related to the injection procedure include redness, itching, pain, tenderness, swelling, bruising, and lumps and bumps, which are common to dermal filler injection procedures, in general. The use of a small gauge needle to deliver VOLUMA with Lidocaine used in this study is intended to minimize tissue trauma. Risks associated with the anesthetic agent include allergic reactions that may manifest as an anaphylactic reaction, skin rash, redness, itching, hives, burning, stinging, swelling, tenderness, and transient loss of skin color. The inclusion of 0.3% lidocaine in the formulation is meant to reduce pain during the injection and this should be taken into account when administering concomitant additional anesthetics.

Treatment using VOLUMA with Lidocaine as an alternative to surgical augmentation rhinoplasty has many benefits. VOLUMA with Lidocaine is less invasive, has much lower rates of infection, has little or no risk of scarring, has no risk of surgery or general anesthesia, and has much shorter recovery times. From a medical aesthetic side, dermal filler could meet customers' high anticipation on the improvement of nose appearance by adjusting injection sites and injected product volume during treatment. Furthermore, as an HA-based filler, VOLUMA with Lidocaine is much safer than fat injections or particulate fillers. It is anticipated that the safety and effectiveness of treatment to the nose are similar to those identified in studies of JUVÉDERM products for similar indications.

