7.4 Treatment Characteristics

Treatment characteristics will be evaluated by collecting information on anesthesia usage (ice, lidocaine cream, local anesthesia, nerve block), injection site (midline dorsum, columella, and anterior spine), injection plane (supraperiosteally and supraperichondrially), injection volume, injection ease (11-point scale where 0 = difficult and 10 = easy), and product moldability (11-point scale where 0 = stiff and 10 = moldable).

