8.3.4 Safety Analyses

ISRs will be summarized by treatment (initial and touch-up), incidence, severity, and duration. Incidence of AEs will be tabulated by primary system organ class (SOC) and by preferred term, and will be tabulated by onset, duration, severity, action taken, relationship to treatment, and outcome. Treatment-related AEs, SAEs, AEs leading to study discontinuations, and deaths will be listed or tabulated. Procedural pain, vital signs and laboratory results will be summarized by frequency distributions or descriptive statistics.

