11.1.8 Relationship to Treatment

Relationship to treatment refers to a determination of the relationship (if any) between an AE and the device or treatment procedure. An AE could be considered treatment-related when, in the judgment of the TI, it is reasonable to believe that the event may have been caused by the device or is associated with the procedure, such as an event that can be attributed to other products, surgical techniques, or medications required specifically for the procedure.

Relationship to treatment must be determined by the TI and cannot be delegated to other study staff.

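### If clock times are used, the VOLUMA-group TEAE definition can drop a first-session anesthetic reaction that starts before the injection and does not later worsen

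*SAP*

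**What the plan says.** - **TEAE rule, SAP 5.6.3.** In the VOLUMA group an event counts once it starts or gets worse "on or after the date (and time, if known) of the initial treatment for treatment group". Getting worse covers both a rise in severity and a change to serious. Controls have a different starting point: their events count if they occur later than randomization.
- **Place of anesthesia, SAP Table 5-6.** Anesthesia type and duration are labelled as pre-treatment, and "Anesthesia duration is computed as injection time minus start of anesthesia administration time". SAP 6.4.2.1 likewise uses the initial injection date as the reference when it imputes AE start dates.
- **Risk, Protocol 2.2.** "Risks associated with the anesthetic agent include allergic reactions that may manifest as an anaphylactic reaction". Protocol 7.4 records which anesthesia was used: ice, lidocaine cream, local anesthesia or nerve block.
- **Relatedness, Protocol 11.1.8.** The treating investigator (TI) may call an event related if it is linked to the procedure; the example given is "such as an event that can be attributed to other products, surgical techniques, or medications required specifically for the procedure".
- **Reporting, Protocol 8.3.4.** "Treatment-related AEs, SAEs, AEs leading to study discontinuations, and deaths will be listed or tabulated". Protocol 11.1.1 collects AEs from consent.
- **SAP outputs.** Table 5-7 is headed as a TEAE summary. The listings in SAP 5.6.3 cover TEAEs, TESAEs, TEAEs leading to discontinuation, and deaths.

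**The concern.** The protocol names the anesthetic as a source of study risk and lets the TI attribute a reaction to the procedure. The SAP's clock can start later than that, at the injection. A reaction in between is collected, may be judged related and may even be serious, yet it falls outside the definition on which the SAP's AE outputs are built. Where the rule bites, it can only remove events, so related first-session events could be understated but not overstated. The same reaction before the optional first treatment of a control participant would be counted, so the two injected cohorts (VITP and VOTP) would follow different rules. Safety is part of the primary objective in SAP 1.1.

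**Working it through.** The plan gives no figure on this point, so the check applies the rule to one event: an anesthetic reaction on the day of treatment, starting after anesthesia and before the injection.

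| Setting | Injection time known | AE onset time known | Worsens after injection | TEAE? |
|---|---|---|---|---|
| VOLUMA group, initial session | yes | yes | no | **no** |
| VOLUMA group, initial session | yes | yes | yes | yes |
| VOLUMA group, initial session | either one unknown | either one unknown | any | yes, by date |
| VOLUMA group, touch-up | any | any | any | yes, after initial treatment |
| Control, optional treatment | any | any | any | yes, after randomization |

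Only the first row is excluded.

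**Are the conditions for that row met?** Injection time and anesthesia start time are evidently recorded, because Table 5-6 subtracts one from the other. AE onset time is not shown to be recorded. SAP 6.4.2 works with year, month and day only, and Table 6-6 calls a date with those three parts complete.

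**Where would the excluded event appear?** It is not a TEAE, so it cannot be a treatment-related TEAE or a TESAE. That removes it from those tables and from the TEAE and TESAE listings. Deaths are reported in any case. The Table 5-7 row for AEs leading to discontinuation is not worded as limited to TEAEs, although the table heading is. SAP 6.2, which records changes from the protocol's planned analyses, does not mention narrowing the reporting of treatment-related AEs and SAEs to treatment-emergent ones.

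**Do the cohorts differ?** In Table 5-1 the Treated Period begins on a date in both cohorts: the initial treatment date for VITP and the optional initial treatment date for VOTP. The difference therefore comes only from the reference to time in 5.6.3.

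**Size of one omitted event.** The denominator is the planned minimum of 120 treatment-group participants (Protocol 5.1 and 8.5).
- Change in rate: 1/120 = 0.0083, or 0.8 percentage points.
- Exact (Clopper-Pearson) 95% interval for 1/120: 0.02% to 4.56%.
- Exact 95% interval for 0/120: 0% to 3.03%, where the upper limit is 1 − 0.025^(1/120).

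**Frequency.** The documents give no rate. Purely as an assumption, suppose a proportion p of 120 first sessions met every condition of the excluded row. The chance of at least one such event is 1 − (1 − p)^120:
- p = 0.5%: 45%
- p = 1%: 70%
- p = 2%: 91%

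The expected counts, 120p, are 0.6, 1.2 and 2.4. These figures show scale and are not estimates.

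**The case against.** The strongest reply is that the rule is date-based and uses time only when it is known. If the AE form has no onset time, every same-day anesthetic reaction is a TEAE and nothing is lost. This stands as a limit on the point, because the documents do not settle it. It does not make the wording right: with onset times the clause excludes such an event, and without them it does nothing.

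A reader might go further and infer four things that the documents do not support.

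- *That anesthetic reactions are absent from every AE output.* The exclusion is a single pattern, and deaths are reported regardless. SAP section 1 also places table and listing specifications in a separate document, which is not available here. The claim can be made only for the outputs described in the SAP text.
- *That such reactions are treatment-related by definition.* Protocol 11.1.8 leaves this to the TI and speaks of medications required for the procedure. Nothing supplied makes pre-injection anesthesia mandatory. Reactions to the lidocaine in the gel itself follow the injection and are counted.
- *That all 120 first sessions are affected.* Only sessions with anesthesia, a reaction before injection, both times recorded and no later worsening could be.
- *That serious reactions would escape oversight.* Protocol 11.3 and 11.4 require all AEs from consent on the eCRF and immediate reporting of SAEs to the sponsor. The gap is in the planned analysis output.

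The time clause also has a purpose, which is to keep same-day events before treatment from being called emergent. That is a reason to prefer a procedure-start anchor over a date-only rule, but not to keep the injection as the anchor.

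**Conclusion.** The gap is real but narrow, and its severity is minor. It rests on reading initial treatment as the injection, which Table 5-6 and SAP 6.4.2.1 support, and on AE onset time being recorded, which is unconfirmed. Under those conditions the SAP definition can omit a reaction that the TI judges related and that Protocol 8.3.4 says will be listed or tabulated. The omission runs in one direction and would treat VITP and VOTP differently. The number of events cannot be estimated from the documents and is probably small. No effectiveness result is touched.

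**What to change.** In SAP 5.6.3, anchor the VOLUMA-group clock at the start of the initial treatment procedure: the start time of pre-treatment anesthesia where it was used, otherwise the injection time. Alternatively, remove the reference to time, so that any event beginning or worsening on the initial treatment date or later is a TEAE. Use the same anchor for VOTP in the Treated Period.

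The cost is a wording change and, for the first option, one derived variable from times already captured for Table 5-6. The date-only option may bring in an occasional same-day event unrelated to the procedure, which the relatedness field would show.
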